### **Statistical Methods**

#### **Primary Analysis**

The primary efficacy outcome measure is the change in CDR-SB from baseline (Week 1) to Week 105. For this primary outcome measure, the difference in mean change from baseline to Week 105 between crenezumab- and placebo-treated patients will be estimated *using* mixed model repeated measures (MMRMs) adjusting for disease severity, *APOEε4* status, geographic region, and the use or non-use of anti-dementia medications at baseline will be used to estimate the mean change from baseline for the primary endpoint. The analysis will include randomized patients *during the Global Enrollment Phase*, with patients grouped according to the treatment assigned at randomization. *Data from patients enrolled after the close of Global Enrollment will be included in analyses separate from the primary analyses.*

The MMRM model will be used to estimate the mean change from baseline for the primary endpoint. The model will include the change from baseline in CDR-SB as the dependent variable. The effects in the model will include baseline score, treatment group, visit, treatment-by-visit interaction and baseline score-by-visit interaction. Visit week will be treated as the repeated variable within a patient. Patient, treatment, and visit week will be treated as class variables. An unstructured variance-covariance structure will be applied to model the within-patient errors; in case of non-convergence, compound symmetry will be used.

The difference in the changes from baseline of each dose group from placebo will be estimated at each time point. The 95% CI and p-value for treatment difference will be presented.

All efforts will be made to minimize missing data. The Sponsor plans to request patients who discontinued early from study treatment *to* return for collection of safety and limited efficacy data until Week 105. To explore the robustness of MMRM results for the primary efficacy conclusions, sensitivity analyses (for example, using multiple imputation and pattern mixture models) will be performed. Descriptive summaries of the number of patients with missing data

and the timing and reasons for discontinuation from study by treatment group will also be provided.

Additional details will be documented in the Statistical Analysis Plan (SAP).

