Biomarker assessments (including positron emission tomography [PET] imaging of amyloid and cerebrospinal fluid [CSF] assessments) have confirmed that pAD represents a relatively early stage in the continuum of AD. Mild AD (mAD) represents a stage of the disease where patients have *not only* cognitive, *but also* clear functional deficits. *The specificity of the clinical diagnosis of mild AD can also be increased by confirming biomarker changes associated with AD (McKhann et al. 2011).* *Classification schemes of AD are an area of ongoing research and are expected to evolve further (e.g., A/T/N; see Jack et al. 2016).*

For potential patients for this clinical trial, evaluations include a thorough clinical assessment as well as measurement of disease relevant biomarkers, i.e., markers of amyloid accumulation in CSF or on brain PET scans. Patients to be enrolled may be at the clinical stage of MCI (pAD) or mild dementia and will have positive biomarkers indicative of AD. (Albert et al. 2011; McKhann et al. 2011).

The rate of AD progression shows great inter-individual variability with survival dependent on many factors, including age at onset. Population studies (Brookmeyer et al. 2002; Larson et al. 2004) suggest a lag of approximately 5 years between symptom onset and diagnosis (Roberson et al. 2005; Waring et al. 2005). Thereafter, the median survival time following a diagnosis of AD depends strongly on the patient's age at diagnosis. The median survival time ranges from 8.3 years for persons diagnosed with AD at age 65 years to 3.4 years for persons diagnosed at age 90 years (Brookmeyer et al. 2002). On average, individuals live for 3–9 years after diagnosis of AD (Helzner et al. 2008), and some survive as long as 20 years.

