### **1.2.2.3 Study ABE4869g**

Study ABE4869g was a Phase II, randomized, double-blind, parallel-group, placebo-controlled study designed to evaluate the safety and efficacy of 68 weeks of crenezumab treatment in patients 50–80 years of age who had been diagnosed with mild to moderate AD (MMSE, 18–26). A total of 444 patients were enrolled and dosed in

the study: 184 patients in an SC cohort, 247 patients in the IV cohort, and 13 patients in a safety run-in cohort.

The study was conducted in two parts. In Part 1, the SC cohort, 184 patients were randomized and dosed in a 2:1 ratio (active: placebo) to receive either crenezumab 300 mg or matching placebo administered via SC injection q2w. In Part 2, the IV cohort, 247 patients were randomized and dosed in a 2:1 ratio (active: placebo) to receive either crenezumab or matching placebo administered via IV infusion q4w. Since the highest single dose assessed during the Phase I study (10 mg/kg IV) did not elicit any dose-limiting toxicities (DLTs), a run-in assessment of the safety and tolerability of multiple monthly IV administrations of 15 mg/kg crenezumab was conducted in a limited number of patients at selected sites prior to initiating full enrollment in the IV cohort in Part 2. On the basis of the outcome of the safety run-in assessment, the dose of crenezumab of 15 mg/kg IV was selected for Part 2. Safety information is provided in Section 1.2.3; full details are provided in the crenezumab Investigator's Brochure.

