### 1.3.2 **Efficacy**

Study ABE4869g did not meet its co-primary efficacy objectives. In the higher dose cohort, a 16.8% treatment effect in the Alzheimer's Disease Assessment Scale-Cognition, 12 questions (ADAS-Cog-12) change score was seen in the mild to moderate AD population (defined as an MMSE score, 18–26) at Week 73 relative to placebo (1.78 point difference; 95% CI, -0.89, 4.44;  $p=0.190$ ) (Cummings et al. 2014; Mackey et al. 2016). The observed treatment effect increased to 23.8% in a prespecified analysis in the mAD population (MMSE score, 20–26; 2.24 point difference; 95% CI, -0.66, 5.15;  $p=0.128$ ) and to 35.4% in a subsequent analysis in patients with an MMSE of 22–26 (3.44 point difference; 95% CI, 0.24, 6.64).

No treatment effect was observed in the Clinical Dementia Rating-Sum of Boxes (CDR-SB) in either the mild to moderate AD population (3.1%; 0.08 point difference; 95% CI, -0.77, 0.92;  $p=0.853$ ) or mild AD population (-1.0%; -0.02 point difference; 95% CI, -1.0, 0.96;  $p=0.964$ ). In an exploratory analysis of a subset of patients with milder AD (MMSE, 22–26), the treatment effects for CDR-SB change from baseline to Week 73 scores relative to placebo increased to 19.6% (1.8 point difference favoring crenezumab; 95% CI, -0.65, 1.52).

In the lower dose (300 mg q2w) SC crenezumab cohort, no treatment effect was observed on the ADAS-Cog-12 in any analysis. A treatment effect toward benefit was observed with crenezumab on the CDR-SB at Week 73. However, in the exploratory analysis (MMSE, 22–26), the treatment effect was in the direction of greater decline. A treatment effect was also observed on the Alzheimer's Disease Cooperative Study-Activities of Daily Living Inventory (ADCS-ADL); however, it was not accompanied by a clear effect on cognition, particularly in the mildest patients. More detail on Phase II results can be found in the crenezumab Investigator's Brochure. When taken together, these data showed a consistent treatment effect only when a 2.5-fold higher exposure of crenezumab was attained (see Section 1.2.5 for further information on the pharmacokinetics of crenezumab).

Data from the Phase II program also showed that patients with milder disease (i.e., MMSE, 22–26) received greater treatment benefit. Similar findings were observed in the

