#### **3.3.1 Rationale for Treatment Duration**

The treatment duration of 100 weeks (26 doses) for assessment of the primary endpoint has been selected on the basis of the mechanism of action of crenezumab that is expected to delay disease progression rather than provide symptomatic improvement over baseline. Any difference between treatment and control will be on the basis of a reduction in the progression of AD over time. Ongoing trials in the AD area have used durations of at least 18 months.

The proposed trial duration is supported by data from Study ABE4869g which demonstrated that the difference in decline between placebo- and crenezumab-treated patients' increased over time until 18 months (the end of the trial). Placebo decline is expected to be greater at 24 months relative to 18 months; this greater decline allows greater potential to demonstrate a treatment effect.

To ensure that evidence relating to *early efficacy* is captured, assessments relevant to the study objectives will be obtained at 6, 12, and 18 months.

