### **6.1 *DETERMINATION OF SAMPLE SIZE***

Determination of sample size is based on patients enrolled in the Global Enrollment Phase. In this study, 750 patients will be enrolled with 375 patients per treatment arm (crenezumab or placebo) during the Global Enrollment Phase. [REDACTED]

The estimate of sample size required to demonstrate efficacy with regard to CDR-SB is based on the following assumptions:

- The mean change in CDR-SB from baseline to Week 105 is 2.6 points in the placebo arm

- A common SD across treatment arms for change from baseline to Week 105 in CDR-SB of approximately 3.07 (this corresponds to a coefficient of variation of 118% for change in CDR-SB from baseline to Week 105 in a prodromal to mild AD population in the placebo arm)
- The dose level has a true effect of a 30% relative reduction in deterioration of CDR-SB
- 35% of randomized patients will dropout by Week 105

This sample size will have 80% power to detect a true treatment effect of 30% relative reduction in deterioration of CDR-SB at 2-sided  $\alpha$  of 0.05.

In the event that the rescue strategy or change in dose is required, the number of patients enrolled in the new dose group and its concurrently enrolled placebo arm will be 750 patients (375 patients per treatment arm) during the Global Enrollment Phase. All patients already enrolled on 60 mg/kg of *study treatment* and corresponding concurrently enrolled placebo patients will be replaced with new patients.

*A blinded assessment of the pooled standard deviation of CDR-SB change from baseline will be performed by the Sponsor at a specified timepoint prior to unblinding. As a result, the sample size may be increased from 750 up to 1126 patients (563 patients per arm). Further details will be described in the Statistical Analysis Plan (SAP). The sample size will not be reduced on the basis of this assessment. Other factors external to the study may also trigger a decision to increase sample size.*

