## **6.4 EFFICACY ANALYSES**

### **6.4.1 Primary Efficacy Endpoint**

The primary efficacy outcome measure is the change in CDR-SB from baseline (Week 1) to Week 105. For this primary outcome measure, the difference in mean change from

baseline to Week 105 between crenezumab- and placebo-treated patients will be estimated. Mixed model repeated measures (MMRMs) adjusting for disease severity, *APOE $\epsilon$ 4* status, geographic region, and the use or non-use of anti-dementia medications at baseline will be used to estimate the mean change from baseline for the primary endpoint. The analysis will include all randomized patients, with patients grouped according to the treatment assigned at randomization.

The MMRM model will be used to estimate the mean change from baseline for the primary endpoint. The model will include the change from baseline in CDR-SB as the dependent variable. The effects in the model will include baseline score, treatment group, visit, treatment-by-visit interaction and baseline score-by-visit interaction. Visit week will be treated as the repeated variable within a patient. Patient, treatment, and visit week will be treated as class variables. An unstructured variance-covariance structure will be applied to model the within-patient errors; in case of non-convergence, compound symmetry will be used.

The difference in the changes from baseline of each dose group from placebo will be estimated at each time point. The 95% CI and p-value for treatment difference will be presented.

All efforts will be made to minimize missing data. The Sponsor plans to request patients who discontinued early from study treatment to return for collection of safety and limited efficacy data until Week 105. To explore the robustness of MMRM results for the primary efficacy conclusions, sensitivity analyses (for example, using multiple imputation and pattern mixture models) will be performed. Descriptive summaries of the number of patients with missing data and the timing and reasons for discontinuation from study by treatment group will also be provided.

Additional details will be documented in the *SAP*.

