#### **6.4.2 Secondary Efficacy Endpoints**

The absolute change from baseline in the continuous secondary efficacy endpoints listed in Section 2 (including cognition endpoints, global endpoints, disease pathology biomarkers, and endpoints that measure other AD symptoms and effects) will be analyzed using an MMRM analysis model similar to that described above for the primary efficacy endpoint.

In order to protect the overall type I error rate for the study when incorporating the hypothesis testing of the primary endpoints and the key secondary endpoints into the analysis, the fixed sequence testing procedure ([Westfall and Krishen 2001](#)) will be used to adjust for multiple comparisons. These endpoints will be tested in the following order:

- 1) Change from baseline to Week 105 in CDR-SB
- 2) Change from baseline to Week 105 in ADAS-Cog-13 *and* ADAS-Cog-11

- 3) *Change from baseline to Week 105 in iADL*
- 4) *Change from baseline to Week 105 in ADCS-ADL total score*

The treatment difference in the primary endpoint (change from baseline to Week 105 in CDR-SB) will be tested at a 2-sided 5% overall significance level using the O'Brien–Fleming boundary. If this test result is statistically significant at either the interim or the final analysis, the treatment difference in change from baseline to Week 105 in ADAS-Cog-13 will be tested at a two-sided 5% significance level. If the treatment effect on ADAS-Cog-13 is statistically significant, the treatment effect on *ADCS-iADL total score* will be tested at a two-sided 5% significance level *and likewise for ADL if iADL is significant*. If any test result is not statistically significant, testing of the subsequent endpoints will not occur.

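### The only fallback for the primary MMRM, compound symmetry, can understate the Week 105 standard error; it is unlikely to be triggered and cheap to replace

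*Combined protocol and SAP*

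**What the plan says.** The primary analysis is an MMRM of change in CDR-SB, and the test of interest is the treatment difference at Week 105. On the within-patient covariance, Section 6.4.1 says: "An unstructured variance-covariance structure will be applied to model the within-patient errors; in case of non-convergence, compound symmetry will be used". The synopsis, under Primary Analysis, has the same rule: "in case of non-convergence, compound symmetry will be used". No intermediate structure, heterogeneous variant or robust standard error is named. Section 6.4.1 leaves further detail to the SAP, and no SAP section with that detail is in the documents reviewed.

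The documents give one SD for change in CDR-SB, in Section 6.1: "A common SD across treatment arms for change from baseline to Week 105 in CDR-SB of approximately 3.07". They give none for earlier visits. Two statements bear indirectly on whether the spread grows. Section 3.3.1 says "Placebo decline is expected to be greater at 24 months relative to 18 months", and Section 1.1 says "The rate of AD progression shows great inter-individual variability with survival dependent on many factors, including age at onset".

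Section 6.4.2 has the continuous secondary endpoints "analyzed using an MMRM analysis model similar to that described above for the primary efficacy endpoint". It does not say whether the fallback carries over. Section 6.7 applies the primary analysis methods to plasma Abeta and MRI volumes.

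**The concern.** Compound symmetry, read in the usual way, has two parameters: one variance for all visits and one correlation for all pairs of visits. The primary contrast sits at the last visit. If patients decline at different rates they spread apart, and the variance of change is largest at Week 105. The single fitted variance then averages the Week 105 value with smaller earlier ones. Dropout worsens this because earlier visits supply more observations. The reported standard error at Week 105 is then too small, and the error runs towards a false positive.

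A false positive on CDR-SB would also open the fixed-sequence tests in Section 6.4.2. A change of structure made after a failed fit on unblinded data would be post hoc, so the rule has to be right in advance.

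**Working it through.** **Inputs from the documents.** 375 per arm, 1:1; SD 3.07 at Week 105; placebo change 2.6; 30% effect; 35% dropout; two-sided 5% (Section 6.1). Post-baseline CDR visits to Week 105 are Weeks 25, 53, 77 and 105 (Appendix 1). An unstructured matrix for four visits has 4 × 5 / 2 = 10 parameters.

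**The plan's own figure.** The effect is 0.30 × 2.6 = 0.78. Evaluable n per arm = 2 × (1.96 + 0.8416)² × 3.07² / 0.78² = 243.2, so 244. With dropout, 244 / 0.65 = 375.4, or 376 against the stated 375. Power with 243.75 evaluable per arm is 80.1%. The design reproduces, with 750 × 0.65 ≈ 488 patients expected at Week 105.

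**Mechanism, by hand.** Take assumed SDs of 2.3, 2.6, 2.85 and 3.07 and no dropout. The compound-symmetry variance is the average: (5.29 + 6.76 + 8.12 + 9.42) / 4 = 7.40, an SD of 2.72. The reported SE is √(2 × 7.40 / 375) = 0.199; the true SE is √(2 × 9.42 / 375) = 0.224. The ratio is 0.886, and type I error = 2{1 − Φ(1.96 × 0.886)} ≈ 8.2%.

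**With dropout.** Two calculations were run. The first is the large-sample limit of the compound-symmetry fit, with linear dropout to 35% and true correlations AR 0.8, AR 0.7 or exchangeable 0.6. The second is a simulation of 3,000 null trials per pattern with the plan's fixed effects (four regions assumed), AR correlation 0.7 and REML. All SDs before Week 105 are assumptions.

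| SD growth | SD at Weeks 25, 53, 77, 105 | Large-sample type I error | Simulated type I error | Mean SE ratio, model/sandwich |
|---|---|---|---|---|
| Constant | 3.07 throughout | 5.0-5.8% | 5.9% | 0.97 |
| Slight (two versions) | 2.75, 2.9, 3.0, 3.07; 2.6, 2.8, 2.95, 3.07 | 6.3-7.9% | 6.9%; 7.3% | 0.93; 0.90 |
| Mild | 2.3, 2.6, 2.85, 3.07 | 8.8-9.7% | 9.6% | 0.86 |
| Moderate | 1.8, 2.3, 2.7, 3.07 | 12.1-13.0% | 12.6% | 0.78 |
| Steep | 1.4, 2.0, 2.6, 3.07 | 15.2-16.0% | 14.4% | 0.73 |
| Extreme | 1.0, 1.6, 2.3, 3.07 | 20.0-20.7% | not simulated | – |

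With 20% dropout the large-sample figures fall only a little: 8.6-9.0% for mild and 11.5-12.0% for moderate growth. A separate calculation with SD proportional to the square root of time and correlation 0.6 gave 14.1% by formula and 13.1% in 2,000 simulated trials.

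**Which patterns are plausible.** One rough clue comes from the Phase II IV cohort at Week 73: "0.08 point difference; 95% CI, -0.77, 0.92" (Section 1.3.2), where "In Part 2, the IV cohort, 247 patients were randomized and dosed in a 2:1 ratio" (Section 1.2.2.3). SE = (0.92 + 0.77) / (2 × 1.96) = 0.431. With 165 and 82 patients, SD = 0.431 / √(1/165 + 1/82) = 3.19 if all were observed, 3.19 × √0.85 = 2.94 at 85%, and 3.19 × √0.70 = 2.67 at 70%. The patterns above whose Week 77 SD lies in that range run from constant to moderate, about 5-13%. Steep and extreme fall outside it.

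**Chance of use.** The unstructured REML fit converged in 200 of 200 trials under each of six patterns, 1,200 of 1,200 in all.

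**Does the remedy work?** Heterogeneous Toeplitz, AR(1) and compound symmetry with model-based SEs gave 4.7-5.1% in every pattern in the large-sample calculation. Plain compound symmetry with a sandwich SE gave 4.6-5.4% in the simulation.

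**The case against.** The strongest reply is that the fallback will almost certainly not be used. Ten covariance parameters from about 750 patients is an easy fit, and it never failed in simulation. That stands, and it sets the urgency. It does not defend the rule, because a fallback matters only when it is used. The convergence check also assumed the full final sample. Section 6.8 allows optional interim analyses with fewer Week 105 values, but their timing is not given, so no failure rate can be put on them.

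Second, variance growth is not documented. Section 3.3.1 speaks of mean decline, and Section 1.1 is general background. This also stands: with a constant SD the loss is at most about one percentage point. The Phase II clue is weak too, since it comes from a more severe population, the number observed is not stated and the interval may be model-adjusted. It gives no support to the figures of 14% and above.

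Third, the SAP may specify a heterogeneous version or a robust SE. That could not be checked. The written rule still names compound symmetry without qualification.

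Fourth, Section 6.4.1 plans sensitivity analyses such as multiple imputation and pattern mixture models, which might expose a result that depends on the fallback. They would not correct the primary p-value.

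**Conclusion.** The point holds as a conditional weakness of low practical urgency. Three things must coincide for harm: the unstructured model fails to converge, compound symmetry is fitted in its homogeneous form with model-based SEs, and the variance of change is largest at Week 105. If they do, the primary test runs above its nominal level: 6-8% for slight growth, 9-10% for mild and 12-13% for moderate. About 5-13% covers the patterns compatible with the one Phase II clue. Unconditionally the type I error stays near 5%. The earlier-visit SDs, the correlations and the dropout shape are assumptions; only the Week 105 SD, the sample size and the 35% dropout come from the plan. For the secondary and biomarker endpoints any effect depends on whether the fallback applies to them and whether their variance grows, and neither is stated.

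**What to change.** Replace the fallback in Section 6.4.1, the synopsis and the SAP, before unblinding, with a rule along these lines:

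*If the unstructured model does not converge, fit heterogeneous Toeplitz, then heterogeneous AR(1), then heterogeneous compound symmetry, and use the first that converges. Use an empirical (sandwich) standard error for any structure other than unstructured. Homogeneous compound symmetry is the last step only, also with the sandwich standard error. The same rule applies to every secondary and biomarker endpoint analysed with this model.*

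Other orderings would serve. What matters is that variances may differ by visit, the order is fixed in advance and the standard error is robust for structured fits.

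The cost is a short text change, with no patients or data. Editing the protocol is formally an amendment under Section 9.6, so the practical route is to put the rule in the SAP now and align the protocol text at the next amendment.

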#### **6.4.2 Secondary Efficacy Endpoints**

The absolute change from baseline in the continuous secondary efficacy endpoints listed in Section 2 (including cognition endpoints, global endpoints, disease pathology biomarkers, and endpoints that measure other AD symptoms and effects) will be analyzed using an MMRM analysis model similar to that described above for the primary efficacy endpoint.

In order to protect the overall type I error rate for the study when incorporating the hypothesis testing of the primary endpoints and the key secondary endpoints into the analysis, the fixed sequence testing procedure ([Westfall and Krishen 2001](#)) will be used to adjust for multiple comparisons. These endpoints will be tested in the following order:

- 1) Change from baseline to Week 105 in CDR-SB
- 2) Change from baseline to Week 105 in ADAS-Cog-13 *and* ADAS-Cog-11

- 3) *Change from baseline to Week 105 in iADL*
- 4) *Change from baseline to Week 105 in ADCS-ADL total score*

The treatment difference in the primary endpoint (change from baseline to Week 105 in CDR-SB) will be tested at a 2-sided 5% overall significance level using the O'Brien–Fleming boundary. If this test result is statistically significant at either the interim or the final analysis, the treatment difference in change from baseline to Week 105 in ADAS-Cog-13 will be tested at a two-sided 5% significance level. If the treatment effect on ADAS-Cog-13 is statistically significant, the treatment effect on *ADCS-iADL total score* will be tested at a two-sided 5% significance level *and likewise for ADL if iADL is significant*. If any test result is not statistically significant, testing of the subsequent endpoints will not occur.

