In addition, the Sponsor may perform an interim assessment for positive efficacy. The type I error rate will be controlled to ensure statistical validity is maintained. Specifically, the Lan-DeMets  $\alpha$ -spending function that approximates the O'Brien-Fleming boundary will be applied to determine the critical value for stopping for positive efficacy at the interim analysis (DeMets and Lan 1994). If the study continues beyond the interim analysis, the critical value at the final analysis would be adjusted accordingly to maintain the protocol-specified overall type I error rate, per standard Lan-DeMets methodology. Control of overall type I error in multiple comparisons of primary and key secondary endpoints are described in Section 6.4. This interim analysis *would also be reviewed by the iDMC, and the Sponsor would remain blinded.* Additional criteria for recommending that the study be stopped for positive efficacy may be added to the iDMC Charter.

*Further details (e.g., timing, data to be reviewed by the iDMC, thresholds, etc.) will be documented in the interim SAP. The interim SAP will be submitted to relevant health authorities at least 2 months prior to the conduct of an interim analysis.*

As information external to the study (e.g., from other compounds) becomes available during the conduct of the study, the Sponsor may implement changes to the protocol to incorporate such learnings into the study, if possible. Such learnings may be concerned with endpoints, biomarkers, and sample size reassessment due to the variability and size of treatment effect observed in other compounds, for example. The Sponsor could

implement such learnings through a protocol amendment while being blinded, but without consultation with the iDMC.

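### If the optional efficacy interim is run, the key secondary endpoints have no group-sequential boundary, so a null ADAS-Cog-13 can exceed 2.5% false benefit by a small amount (about 2.5–3.7% at the planned CDR-SB effect, under assumed timing and correlation)

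*Combined protocol and SAP*

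**What the plan says.** Section 6.4.2 sets up a fixed-sequence procedure with a stated aim: "In order to protect the overall type I error rate for the study". CDR-SB comes first and "will be tested at a 2-sided 5% overall significance level using the" O'Brien-Fleming boundary. If CDR-SB is "significant at either the interim or the final analysis, the treatment difference in change from baseline to Week 105 in ADAS-Cog-13 will be tested"; the level for that test is two-sided 5%. The instrumental ADL score and then the ADCS-ADL total follow, each at two-sided 5%. The gate is strict: "If any test result is not statistically significant, testing of the subsequent endpoints will not occur". The word for an overall level, and a boundary, appear for CDR-SB and for no secondary.

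Section 6.8 makes the efficacy interim optional: "In addition, the Sponsor may perform an interim assessment for positive efficacy". The Lan-DeMets spending function there "will be applied to determine the critical value for stopping for positive efficacy at the interim analysis", with a matching adjustment of the final critical value. For the secondaries it points back: "Control of overall type I error in multiple comparisons of primary and key secondary endpoints are described in Section 6.4". Timing and thresholds are left to a separate plan: "The interim SAP will be submitted to relevant health authorities at least 2 months prior to the conduct of an interim analysis".

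**The concern.** A fixed sequence at full level is valid when every endpoint is tested at one analysis. With two possible looks, the CDR-SB data decide when ADAS-Cog-13 is tested. If CDR-SB truly works and ADAS-Cog-13 is null but positively correlated with it, an early CDR-SB crossing tends to fall at a moment when ADAS-Cog-13 also looks favourable by chance. ADAS-Cog-13 then meets 1.96 rather than a boundary that allows for two looks.

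At stake is a benefit claim on ADAS-Cog-13 after an early crossing. Section 6.4.2 already fixes the secondary level for that case and Section 6.8 refers back to it. An interim SAP that chose a stricter secondary threshold would therefore depart from the protocol text.

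**Working it through.** **Inputs from Section 6.1.** Placebo change 2.6 points, 30% relative reduction, SD 3.07, 375 per arm, 35% dropout, two-sided 5%, 80% power.

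**The plan's own figure.**
- Effect: 0.30 × 2.6 = 0.78.
- Completers per arm: 375 × 0.65 = 243.75.
- SE: 3.07 × √(2/243.75) = 0.278.
- Drift: 0.78/0.278 = 2.80. Power: Φ(2.80 − 1.96) ≈ 80.1%. The stated 80% is reproduced.

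**Assumptions not in the documents.** One efficacy interim at information fraction t; the same t for both endpoints; correlation ρ between the CDR-SB and ADAS-Cog-13 statistics; O'Brien-Fleming-type Lan-DeMets bounds c₁, c₂ for CDR-SB.

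**Model.** The CDR-SB statistics X₁, X₂ have means θ√t and θ. The ADAS-Cog-13 statistics Y₁, Y₂ have mean 0. Correlations: X₁ with X₂ and Y₁ with Y₂, √t; X with Y at the same look, ρ; across looks, ρ√t. Under the plan's rule:

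false benefit = P(X₁ > c₁, Y₁ > 1.96) + P(X₁ ≤ c₁, X₂ > c₂, Y₂ > 1.96).

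The two-sided error adds the same terms for Y < −1.96. Each setting used 2 million simulated trials (simulation SE about 0.01 percentage points). The planned effect is θ = 2.80; the worst case is taken over θ from 1 to 7.

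| t | CDR-SB two-sided p, interim / final | CDR-SB crosses at interim (plan) | False benefit at plan, ρ = 0.5 / 0.7 / 0.9 | Worst over CDR-SB effects | Two-sided error at plan | Worst two-sided |
|---|---|---|---|---|---|---|
| 1/3 | 0.0002 / 0.0499 | 1.8% | 2.7 / 2.9 / 3.4% | 3.0–3.8% | 3.3–3.6% | 5.4–5.7% |
| 0.4 | 0.0008 / 0.0497 | 5.7% | 2.8 / 3.2 / 3.7% | 3.0–3.7% | 3.5–3.7% | 5.0–5.2% |
| 0.5 | 0.0031 / 0.0490 | 16% | 2.9 / 3.1 / 3.2% | 2.9–3.5% | 3.2–3.7% | 4.6–4.8% |
| 0.7 | 0.0148 / 0.0455 | 46% | 2.6 / 2.6 / 2.5% | 2.6–3.1% | 2.5–3.4% | 5.0% |

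**Weaker correlation.** At the planned effect, ρ = 0.3 gives 2.4–2.6% and ρ = 0 gives 2.0%. Over all CDR-SB effects the worst is 2.8% at ρ = 0.3, and there is no excess at ρ = 0.

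**Where two-sided 5% is passed.** At t = 1/3 this first happens at θ of about 4.0, a reduction of 30% × 4.0/2.80 = 43%. At t = 0.4 the peak is near 1.7 times the planned effect, a reduction of about 51%.

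**Next in sequence.** A null instrumental ADL score shows no excess if ADAS-Cog-13 is also null (0.5–2.2% at plan, for t = 1/3, 0.5 and 0.7). If ADAS-Cog-13 has an effect as strong as the planned CDR-SB effect, the rate is 2.5–3.3% at plan and at most 3.8%. ADCS-ADL was not simulated.

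**The case against.** Four points on the other side are fair.

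- **The plan's own limit holds at the planned effect.** Section 6.4.2 sets ADAS-Cog-13 at two-sided 5%, and the two-sided error there is at most 3.7% in the table. The 2.5% benchmark is half of that level and is not stated in the documents. This stands and limits the claim. It does not remove it: the total is low because the CDR-SB gate cuts the harm tail, which gives no protection against a false benefit claim.
- **No scheduled analysis is affected.** The efficacy interim is optional, Section 6.8 promises type I error control in general terms, and an interim SAP must precede any look. This also stands. It does not close the gap, because for the key secondaries Section 6.8 returns the reader to Section 6.4.
- **The excess is small and needs four conditions together:** an efficacy interim, a real CDR-SB effect, a null ADAS-Cog-13, and substantial correlation. Where early crossing is likely (46% at t = 0.7), the planned-effect excess is only about 0.1 points. The largest excesses come with early looks, where crossing is rare.
- **Choosing one boundary shape is a preference.** Agreed: either common shape will do if it is named in advance.

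A reader might infer that the trial's error control is already broken, that the overall 5% is exceeded under the planning assumptions, or that a failed secondary may be tried again at the final analysis. The documents support none of these. There is no scheduled efficacy look, two-sided error is within 5% at the planned effect, and the text provides for no retest.

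**Conclusion.** The concern holds as a minor, conditional point. Section 6.4.2 claims overall type I error protection but gives a boundary to CDR-SB alone, and Section 6.8 does not supply the rest. If an efficacy interim is run, CDR-SB truly works and a correlated ADAS-Cog-13 is null, false benefit at the planned effect is about 2.5–3.7% against 2.5%. That range rests on one O'Brien-Fleming-type interim at fraction 1/3 to 0.7, correlation 0.5 to 0.9 and equal information fractions. It is not a bound: other CDR-SB effects give up to 3.8% in the same settings.

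At the planned effect the excess is negligible for a look at fraction 0.7 or later, or for correlation 0.3 or less. Two-sided error passes 5% only with an early look and a CDR-SB effect well above plan: about 5.1% at fraction 0.4 and up to 5.7% at 1/3. With no efficacy interim the rule is valid as written. The CDR-SB test itself is not in question.

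**What to change.** Amend Section 6.4.2, and mirror the text in the interim SAP before any unblinded efficacy look:

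- If no efficacy interim is performed, each key secondary is tested in sequence at two-sided 5%, as now.
- If one is performed, each key secondary is tested once, in sequence, at the look where CDR-SB crosses. It is tested against its own Lan-DeMets boundary (Pocock-type or O'Brien-Fleming-type, named in advance) at overall two-sided 5%, computed from that endpoint's own information fractions. A secondary that fails is not retested.
- If ADAS-Cog-11 stays in step 2, state its place in the sequence, because the testing paragraph names only ADAS-Cog-13.

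A rejection then requires the secondary to cross its own boundary, so false benefit cannot exceed 2.5% at any correlation. This needs the right information fractions. If 0.5 were used when the true value was 0.4, or 0.7 when it was 0.5, a Pocock-type boundary taken alone would have one-sided error of 2.6% or 2.7%. In the settings checked, with equal fractions, the Pocock-type rule gave at most 2.2%.

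No extra patients are needed, and nothing changes without an efficacy interim. With one, the Pocock-type two-sided thresholds (interim / final) are 0.023/0.033 at fraction 1/3, 0.031/0.028 at 0.5 and 0.039/0.024 at 0.7. The table gives ADAS-Cog-13 power over both looks, for an effect as strong as the planned CDR-SB effect and correlation 0.5–0.9:

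| Fraction | Unadjusted | Pocock-type | O'Brien-Fleming-type |
|---|---|---|---|
| 1/3 | 69–75% | 65–72% | 67–74% |
| 0.5 | 67–75% | 61–70% | 60–71% |
| 0.7 | 64–75% | 60–69% | 56–68% |

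The loss is about 3–6 points for Pocock-type and 1–8 points for O'Brien-Fleming-type.
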